Study Protocol for: Imaging della Placca Carotidea (IMPLAC) study

Funding: Italian Ministry of Health

Grant number: GR-2009-1608780

NCT number: NCT03333330

The aim of the present study will be to evaluate the relation between carotid artery plaque characteristics, cardiovascular risk factors and brain atrophy/WMH burden analyzed, quantitatively as number and volume of lesions and as brain volumes, and progression over 18 months of follow up in subjects asymptomatic for cerebrovascular disease with a carotid artery stenosis <70%. We will characterize the carotid artery plaque using ultrasound, contrast enhanced ultrasound and computed tomography angiography. Cerebral volumes and WMH were evaluated quantitatively using brain magnetic resonance imaging. All baseline imaging and clinical evaluation will be performed within one month from enrollment.

Patient enrollment

Asymptomatic subjects with carotid stenosis <70% according to Doppler velocity measurement presenting to the Neurophysiology and the Vascular Surgery outpatient clinics of Ospedale San Raffaele (Milan, Italy) will be evaluated for enrollment. Exclusion are: age <18 or > 85 years, pregnancy, history of allergic diathesis, previous stroke or transitory ischemic attack, previous carotid endarterectomy (CEA) or stenting, vasculitis, history of alcohol or drug abuse, life expectancy of <18 months, presence of cognitive impairment preventing the patient from providing informed consent, history or current AF or previous cardiac surgery as potential confounding causes of cerebral ischemic damage. These criteria were selected to limit the inclusion of potential confounding causes of cerebral damage. Table 1 provides a schematic for the exclusion criteria. All subject will have to sign a written informed consent to take part in the study.

Exclusion criteria for the IMPLAC study

Age <18 or >85 years

Contraindications to CTA (eGFR<60 mL/min; history of allergic reaction to iodinated contrast media)

Pregnancy or child-bearing potential

Specific contraindication to MRI:

- Claustrophobia
- Sickle cell anemia
- Systemic mastocytosis
- Implanted cardiac devices (PM, ICD)
- Vascular clips
- Vertebral distractors
- Infusion pumps
- Neurostimulators
- Liquor derivations
- Any device which could be dispositioned in the presence of a strong magnetic field

Dementia

Life expectancy less than study follow up (18 months)

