A patient will be defined as suffering from hypertension in compliance with the definition of the European Society of Cardiology (ESC)/European Society of Hypertension, i.e. systolic blood pressure (BP) ≥ 140 mmHg or diastolic BP ≥ 90 mmHg. A clinical history of hypertension with current BP medication will also be considered diagnostic. A subject will be considered as suffering from resistant hypertension in the presence of uncontrolled hypertension or a history of poorly controlled BP and a current BP treatment with at least three drugs including a diuretic. A fasting blood glucose > 126 mg/dL, a glycaemia > 200 mg/dL two hours after an oral glucose load of 75g, HbA1C levels over 6.5% or current treatment with oral anti-diabetic agents or insulin will be taken into account for the diagnosis of diabetes. Hypercholesterolemia is defined according to ESC guidelines: total cholesterol ≥ 200 mg/dL and /or LDL-C ≥ 120 mg/dL. Current lipid lowering therapy will also be taken into consideration for the definition of hypercholesterolemia. To evaluate the cardiovascular risk profile of our patients, we employed the Framingham Risk Score (FRS) to estimate the probability of a first acute myocardial infarction at 10 years. The variables taken into consideration are age, systolic BP, current smoke, BP medication, total cholesterol and HDL-C. A patient with a FRS $> 20\%$ is considered at high risk. The presence of diabetes mellitus or manifest cardiovascular disease confer high risk independently from calculated FRS.

Carotid artery ultrasound

All patients will undergo bilateral Duplex ultrasound evaluation of the carotid arteries. Examinations will be performed using a dedicated ultrasonography equipment (Logiq S8, GE Healthcare, UK) with a 7-MHz linear probe (7L, GE). The patient is positioned supine, with the head tilted 45° toward the side opposite to the one being imaged. A transverse sweep is recorded from the lower neck to the common carotid artery (CCA) bifurcation into the external carotid artery (ECA) and internal carotid artery (ICA) in order to identify atherosclerotic lesions, defined as focal lesions exceeding 2 mm in thickness. Each of the segments is identified according to the Rotterdam Study criteria: the 15 mm caudal to the bifurcation was defined as carotid bulb, while cranially we identified ICA and ECA. Longitudinal images are then recorded using anterior, posterior and lateral (45°) views.

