Milan, 1st April 2012

Statistical plan for: Imaging della Placca Carotidea (IMPLAC) study

Funding: Italian Ministry of Health

Grant number: GR-2009-1608780

NCT number: NCT03333330

The primary outcome of the study will be the presence of white matter hyperintensities (WMH) progression (defined as the appearance of at least 1 new lesion on cerebral magnetic resonance imaging) after 18 months. The secondary endpoint will be the reduction of brain volumes (total volume, grey matter volume and white matter volume) at 18 months. Our primary analysis will be focused at identifying independent predictors of WMH among clinical characteristics of the patients as well as plaque related variables, including volumetric measures of plaque volumes and characteristics of plaque vulnerability, such as presence of ulcer or neovascularization. All continuous variables will be tested for normality using Shapiro-Wilk normality test and are expressed as mean±standard deviation (SD) or median [interquartile range (Q1-Q3)] as appropriate. Categorical variables are summarized as absolute frequency (percentage). Group differences will be tested using unpaired t test, Mann-Whitney U test or Wilcoxon matched pair signed rank test. Spearman's rank correlation coefficient was used to assess statistical dependence. Association between categorical variables was tested using Chi-squared test or Fisher's exact test as appropriate. A $p<0.05$ was considered significant. A multivariate regression analysis was then performed to identify factors that independently influence the burden of WMH in terms of number and volume. All variables associating to WMH burden with a $p<0.10$ will be included in the multivariable model. Our main hypothesis is that subjects with a high plaque burden will experience the highest progression of WMH. We calculated the sample size for multivariate logistic regression analysis with a power of 0.8 and an alpha of 0.05. We will analyze the highest tertile of carotid plaques burden in terms of plaque volume versus others (see Sillesen, 2012). By this definition, the prevalence of high burden atherosclerosis will be 33%. We estimated a clinically relevant probability of progressing in terms of WMH in the high burden group to be 50%, while subjects without high burden plaques are estimated to progress in terms of WMH as the general population with carotid atherosclerosis in a similar time frame. This probability would be estimated to be around 15% (see Dufoil, 2005 and Pico, 2002). The estimated sample size would be 58 individuals. All statistical analyses will be performed using GraphPad Prism 5 (GraphPad Software Inc., La Jolla, USA), IBM SPSS Statistics 20 (IBM, Armonk, USA) or R v3.1.2.

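### The only covariate rule in the SAP is for WMH burden; the logistic model of WMH progression that sizes the study has no covariate specification, and its 0.80 power is unadjusted

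*SAP*

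**What the plan says.** The SAP is one unsectioned text. It defines the endpoint first: "The primary outcome of the study will be the presence of white matter hyperintensities (WMH) progression", meaning one or more new lesions on MRI at 18 months. The hypothesis concerns the same variable: "Our main hypothesis is that subjects with a high plaque burden will experience the highest progression of WMH".

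The sample-size text is also about progression: "We calculated the sample size for multivariate logistic regression analysis with a power of 0.8 and an alpha of 0.05". It compares the top tertile of plaque volume (33% of patients) with the rest, assumes 50% and 15% progress, and arrives at 58 individuals.

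The regression described as an analysis has a different outcome: "A multivariate regression analysis was then performed to identify factors that independently influence the burden of WMH in terms of number and volume". The entry rule follows directly: "All variables associating to WMH burden with a $p<0.10$ will be included in the multivariable model".

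The primary-analysis sentence speaks of independent predictors of WMH without saying whether progression or burden is meant. Its candidates are clinical characteristics and plaque variables, including "characteristics of plaque vulnerability, such as presence of ulcer or neovascularization". The protocol has no statistical section. Its opening aim treats burden and progression as separate things: "brain atrophy/WMH burden analyzed, quantitatively as number and volume of lesions and as brain volumes, and progression over 18 months of follow up".

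**The concern.** Burden (how many lesions, how much volume) and progression (any new lesion, yes or no) are different variables. The model that answers the main hypothesis appears only in the sample-size text, as an exposure, two event rates and a model type. Its covariates are not given, nor is it said that plaque volume stays in whatever the screen shows.

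An analyst looking for a covariate rule will find only the burden rule. Applied to progression, it would choose adjustment variables by their association with another outcome, would fix the set only after the data are seen, and would put no limit on how many terms share a small number of events. What is at stake is chiefly the plaque-burden odds ratio, the estimate that answers the main hypothesis. In addition, the power statement is attached to a multivariable analysis, so a reader will assume it allows for covariates.

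**Working it through.** **1. Reproduce N = 58.** Inputs from the SAP: B = 0.33 (high burden), p1 = 0.50, p0 = 0.15, alpha 0.05, power 0.80. Two-sided testing is my assumption. Overall rate P = 0.33 × 0.50 + 0.67 × 0.15 = 0.2655. The sample-size formula for logistic regression with one binary covariate is

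N = [z(alpha) × √(P(1−P)/B) + z(power) × √(p0(1−p0) + p1(1−p1)(1−B)/B)]² / [(p1−p0)²(1−B)]

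- First root: √(0.2655 × 0.7345 / 0.33) = 0.7687.
- Second root: √(0.1275 + 0.25 × 0.67/0.33) = 0.7969.
- Denominator: 0.1225 × 0.67 = 0.0821.
- Two-sided: (1.960 × 0.7687 + 0.842 × 0.7969)² / 0.0821 = 57.8, so **58**.
- One-sided (1.645): 45.6, so 46. A one-sided test reaches 57.8 only if covariates are assumed to explain 21% of exposure variance (45.6/0.79).

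So the stated figure matches a two-sided test with no allowance for other covariates.

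**2. Power once covariates enter.** Replace 58 by 58 × (1 − R²), where R² is the share of exposure variance that the covariates explain. The documents give no R²; 10% and 20% are assumed.

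| R² | Effective N | Two-sided power |
|---|---|---|
| 0 | 58 | 0.80 |
| 0.10 | 52.2 | 0.76 |
| 0.20 | 46.4 | 0.71 |

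**3. Expected progressors.** 58 × 0.33 × 0.50 = 9.6 in the high-burden group and 58 × 0.67 × 0.15 = 5.8 in the others, **15.4** in all. Events per model term: 15.4 with one term, 7.7 with two, 5.1 with three, 3.1 with five. At the conventional 5 to 10 events per term (an assumption), this supports 1.5 to 3.1 terms, plaque volume included.

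**4. How many variables might a p<0.10 screen admit?** The SAP gives no number. Counting the measurements the documents mention, besides plaque volume:

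- protocol clinical and biochemical section: 15;
- carotid ultrasound: 5;
- contrast ultrasound: 1;
- CTA: 2;
- ulcer, from the SAP: 1.

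The total is at most about 24. Many overlap (several blood pressure items, several lipid items, and the Framingham score beside its own inputs), so a working list could be much shorter. With 24 candidates, chance alone admits 24 × 0.10 = 2.4 on average. If 4 to 8 correlate with burden at an assumed r = 0.3, it admits 5.0 to 7.6. With 12 candidates, 4 of them correlated, it admits 3.8.

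**5. Effect on the odds ratio.** True value: (0.50/0.50)/(0.15/0.85) = 5.67. Illustrative simulations used 19 and 39 patients, with covariates that have no effect on progression. Ranges are across separate runs.

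| Covariates in the model | Median ordinary logistic odds ratio |
|---|---|
| none | 6.1 |
| one fixed | 6.1–6.2 |
| two fixed | 6.1–6.5 |
| five fixed | 7.5 |
| eight fixed | 9.0–9.1 |
| screen, 24 candidates, none correlated | 6.3–6.5 |
| screen, 12 candidates, 4 correlated | 6.9 |
| screen, 24 candidates, 4 correlated | 7.4–7.5 |
| screen, 24 candidates, 8 correlated | 8.4–9.1 |

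Under the screen, the likelihood-ratio rejection rate at the planned effect stays at 0.78–0.80. With no true effect it is about 0.063 with no covariate and 0.085 with eight fixed covariates. Firth-penalised fits give a median of about 5.3–5.7 in every setting.

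**The case against.** The strongest reply is that the SAP never applies the p<0.10 rule to progression. The rule follows the burden regression and refers to it. Burden is measured in every patient, so the limit of 15 events does not touch that model. This stands: a reader might infer that the SAP prescribes an overfitted primary model, and it does not. What remains is that the progression model then has no covariate rule at all.

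The size of the harm is also uncertain. The candidate count is my tally of overlapping measurements, the correlations are assumed, and the low end of the screen range is no worse than two fixed covariates. The simulated covariates are unrelated to plaque volume, whereas total plaque area and stenosis probably are not. All of this stands and makes the inflation conditional.

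Two further inferences fail. The SAP does not omit the logistic model: the sample-size text names it and its exposure. Nor is 58 an arithmetic error: it reproduces.

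Finally, the SAP calls the search for independent predictors its primary analysis, and small event numbers do not by themselves require that aim to be demoted. I accept that. Penalised fitting removes most of the odds-ratio bias, though not the data-driven selection.

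**Conclusion.** The concern holds as a gap in specification with a conditional consequence, and it should be fixed.

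Two things are established from the documents. The only written regression and the only entry rule are for burden, while endpoint, hypothesis and sample size are for progression. And 58 with power 0.80 is an unadjusted figure if the test is two-sided, although it is attached to a multivariable analysis. With covariates explaining an assumed 10–20% of exposure variance, power would be about 0.76–0.71.

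The overfitting is conditional on the burden rule being carried over. Then, with 15.4 expected progressors, the median odds ratio runs from about 6.3 to 9.1 against a true 5.67. About 6.1 of that arises with no covariate at all, and clear inflation needs roughly four or more covariates to enter. A reader might infer that the screen also costs much power at the planned effect; these simulations do not show that. The harm is mainly to the estimate and to its pre-specification.

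**What to change.** Change the SAP wording as follows.

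1. State the primary model: logistic regression of WMH progression at 18 months (yes/no) on top-tertile plaque volume versus the rest, with plaque volume forced in. Report the odds ratio with 95% CI, unadjusted and adjusted.
2. Do not use the p<0.10 burden screen for this model. Name one covariate, at most two, in advance from data already collected. Two covariates meet only the lenient limit of 5 events per term, and even one exceeds the limit of 10, which is why the unadjusted result belongs beside the adjusted one. Age is one option. The Framingham score is another, but it already contains age, and used as a continuous score it leaves out conditions the protocol handles separately: "The presence of diabetes mellitus or manifest cardiovascular disease confer high risk independently from calculated FRS".
3. Fit this model, and any wider multi-predictor model of progression, by Firth logistic regression. The multi-predictor aim may stay, with a sentence saying that its data-selected results do not replace the pre-specified plaque-volume estimate.
4. State the sidedness. If two-sided, describe 0.80 power at N = 58 as unadjusted and give the adjusted range with its assumed R².

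The cost is text only, with no new data or enrolment. The downsides are some residual confounding with so few covariates and a slightly less favourable power statement.

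### The primary predictor search enters every variable at p<0.10 from an unlisted pool and claims at p<0.05 with no familywise or overlap rule; its reach over the progression model is unclear

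*SAP*

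**What the plan says.** The SAP is a single section. It states the aim of the primary analysis as follows: "Our primary analysis will be focused at identifying independent predictors of WMH among clinical characteristics of the patients as well as plaque related variables". The plaque variables are described only by example: "including volumetric measures of plaque volumes and characteristics of plaque vulnerability, such as presence of ulcer or neovascularization". The modelling sentence is about burden: "A multivariate regression analysis was then performed to identify factors that independently influence the burden of WMH in terms of number and volume". The selection rule follows directly: "All variables associating to WMH burden with a $p<0.10$ will be included in the multivariable model". Significance is set at p<0.05 throughout.

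The same section names one main hypothesis, and it concerns progression: "Our main hypothesis is that subjects with a high plaque burden will experience the highest progression of WMH". The exposure is specific: "We will analyze the highest tertile of carotid plaques burden in terms of plaque volume versus others". The study is sized on that contrast: "We calculated the sample size for multivariate logistic regression analysis with a power of 0.8 and an alpha of 0.05". The primary outcome is binary, the appearance of one or more new lesions by 18 months. The protocol's opening paragraph also lists burden and progression as separate items: "brain atrophy/WMH burden analyzed, quantitatively as number and volume of lesions and as brain volumes, and progression over 18 months".

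Neither document lists the candidates, caps the number of model terms, controls multiplicity, or says how overlapping measures are handled. Neither says that the plaque-volume tertile is tested first or forced into the model.

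**The concern.** Two things are at stake.

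The first is false discovery. A search over many variables, each claimed at p<0.05, can name some chance predictor far more often than 1 time in 20. Here that search is called primary.

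The second is overlap. The protocol measures the same disease in several ways. Stenosis is graded by Doppler velocity, by ECST on duplex, and by NASCET and ECST on CTA. Plaque burden is recorded as total plaque area, number of involved segments and CTA plaque volume (sections on carotid artery ultrasound and CTA). The Framingham score is built from age, systolic pressure, smoking, blood-pressure medication, total cholesterol and HDL-C, most of which are also recorded separately (section on clinical evaluation). Nothing stops all of these from entering one model. If that happens in the progression model, plaque volume is adjusted for other measures of itself, and the power behind n=58 is lost.

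**Working it through.** **1. The plan's own figure.** Inputs from the SAP: high-burden prevalence B = 0.33, progression 50% against 15%, alpha 0.05 (taken as two-sided), power 0.80. Overall rate P = 0.33 × 0.50 + 0.67 × 0.15 = 0.2655. The formula for logistic regression on one binary covariate is

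n = [1.960 × √(P(1−P)/B) + 0.842 × √(0.15 × 0.85 + 0.50 × 0.50 × 0.67/0.33)]² / [(0.35)² × 0.67]

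= (1.507 + 0.671)² / 0.0821 = 57.8, so 58. The figure reproduces as a single unadjusted contrast. A two-proportion calculation at 58 gives power 0.803. Expected progressors: 58 × 0.2655 = 15.4.

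**2. How many candidates (assumption).** The documents give no count. Listing what they measure gives 27:
- 14 clinical: age, hypertension, resistant hypertension, diabetes, hypercholesterolaemia, smoking, systolic and diastolic pressure, glycaemia, four lipids, Framingham score.
- 13 plaque: CC-IMT, Doppler stenosis, duplex ECST, total plaque area, segments, echogenicity, CEUS status, number of CEUS-positive plaques, CTA NASCET, CTA ECST, plaque volume, composition, ulcer.

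Keeping one measure per overlapping group and dropping the Framingham score leaves 10.

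**3. Simple bounds.** With 27 null candidates, 27 × 0.10 = 2.7 pass the screen on average. For 27 independent tests at 0.05 with no joint model, 1 − 0.95^27 = 75%; for 10, 1 − 0.95^10 = 40%.

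**4. The rule as written, simulated.** n = 58, event rate 26.55%, all candidates null, enter at p<0.10, claim at p<0.05 in the joint model. A linear version stands in for lesion number and volume. Entries are the familywise chance of at least one false predictor for one outcome. Ranges come from separate runs, some with continuous and some with mixed continuous and binary candidates.

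| Candidates and correlation (assumed) | Logistic | Linear |
|---|---|---|
| 27, independent | 58–63% | 64–68% |
| 27, two blocks, r=0.3 | 43–46% | 48% |
| 27, two blocks, r=0.5 | 26–34% | 33% |
| 27, two blocks, r=0.7 | 17–18% | 18% |
| 27, one block, r=0.3 | 31–36% | 32–42% |
| 27, one block, r=0.7 | 9% | not run |
| 10, independent | 32–34% | 38% |
| 10, two blocks, r=0.3 | 28–29% | 33% |
| 10, two blocks, r=0.5 | 20–22% | 25% |
| 10, two blocks, r=0.7 | 12–15% | 17% |

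The lowest setting tried with 10 candidates gave 9%. A finer structure of nine small domains, with 27 candidates and a logistic model, gave 52% (within-domain 0.3, between 0.1), 42% (0.5, 0.1), 26% (0.7, 0.3) and 13% (0.8, 0.5). In that structure, modelling number and volume together raised the chance of a false predictor in either to 28% to 86%, under assumed outcome correlations.

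**5. Power of the main contrast.** The exposure is the top 19 of 58 on a latent burden, and the outcome depends only on the tertile (50% against 15%). Alone, power is about 79%. With three further measures in the model, each correlated r with the latent burden:

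| r (assumed) | Power |
|---|---|
| none added | 79% |
| 0.3 | 71–75% |
| 0.5 | 61–64% |
| 0.7 | 45–49% |

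The second to fourth rows apply only if the p<0.10 rule governs the progression model and such measures enter.

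**The case against.** The strongest reply is that the main hypothesis is protected. The SAP names one exposure with its alpha, power and sample size. A test of that contrast alone keeps its nominal error and its planned power. A reader might infer that the p<0.10 rule undermines this test. The documents do not support that: the rule is worded for burden, directly after a sentence on number and volume, and no sentence extends it to progression. Equally, no sentence excludes progression or states any other covariate rule for the logistic model. The power loss is therefore conditional.

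Second, a reader might infer that each reported p-value is itself inflated. It is not, in the unconditional sense. In all-null runs with 27 candidates, each variable's own chance of being falsely claimed was 0.4% to 3.7%. The inflation is familywise and comes mainly from the number of candidates. This objection stands, and the point is worded accordingly.

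Third, the count and correlations are assumed, some of the 27 are defined from one another, and all-null is a limiting case. This also stands, so no single percentage should be quoted as the plan's error rate. Values below 9% occur too: one common correlation of 0.6 to 0.8 across all 27 gave 3% to 15%. That is hard to credit for a pool mixing lipids, smoking, diabetes and plaque echogenicity.

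Finally, familywise control in an observational search is partly a matter of preference. That would answer the point if the search were labelled exploratory, but the SAP calls it primary.

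**Conclusion.** The concern holds in limited form. The search called primary has no closed candidate list, no multiplicity rule and no overlap rule. Its familywise chance of a false independent predictor, for one outcome with all candidates null, is about 9% to above 60% over the plausible settings tried, and about 17% to 46% with 27 candidates in two moderately correlated blocks. Cutting the list to 10 does not by itself restore 5%: those runs gave 9% to 34%.

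It is unclear whether the rule reaches the progression model. If it does not, the tertile contrast keeps its 79% to 80% power. If it does, the loss could be a few points or more than 30, depending on how strongly the added measures track plaque volume. The documents do not establish that the main hypothesis test is compromised. This is a cheap improvement to the SAP, not a defect that invalidates the design.

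**What to change.** In the SAP:

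- Name the confirmatory test as logistic regression of WMH progression (one or more new lesions at 18 months) on top-tertile plaque volume. Use a very small covariate set fixed in advance, for example age, rather than one chosen by p<0.10. Put no other plaque-burden or stenosis measure in that model. Report the unadjusted estimate alongside.
- State which outcomes (progression, number, volume) the p<0.10 rule applies to.
- Keep the predictor search, labelled exploratory, with a listed candidate set, one measure per overlapping group, no Framingham score together with its components, and estimates with confidence intervals.

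The cost is wording; no new patients, data or software are needed. The real downside is that fewer variables can be claimed as independent predictors, because the search loses its primary label. Fixed covariates also cost some power. Against 78.6% unadjusted, one covariate correlated 0.3 with plaque burden gave 76.5%, a loss of about 2 points. At 0.5 it gave 73.2% if prognostic (odds ratio 1.5 per SD) or 70.5% if not, a loss of 5 to 8 points. Two covariates cost about 5 to 6 points at 0.3 and 11 to 17 at 0.5, which is why the set should stay very small.

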History of drug abuse, alcohol abuse or any psychiatric or social condition which may contraindicate the participation to a clinical study

Vertebral artery occlusion
Previous revascularization of the carotid artery
Current anti-coagulation
Atrial fibrillation not necessitating anticoagulation
Known PFO necessitating anti-platelet treatment
Previous cerebrovascular accidents
Previous infections to the CNS
Previous surgery to the CNS
History of anoxic damage to the CNS
Previous cardiac surgery or positioning of intracardiac devices (excluded coronary stents)
History of autoimmune vasculitis

Table 1. Exclusion criteria for the IMPLAC study. CTA: computed tomography angiography. CNS: central nervous system. PFO: patent foramen ovale.

Clinical evaluation and biochemical measurements

At enrolment, all subjects will undergo clinical evaluation including careful medical history, and physical examination, comprising cardiac auscultation for the detection of irregular heartbeat and two blood pressure measurements. The history will be focused on the identification of cardiovascular risk factors (CVRFs) and of current treatment. Whole blood will be collected on the same day using two 5mL EDTA-anticoagulated vacutainer tubes. For each patient, glycaemia, total cholesterol, high-density lipoprotein cholesterol (HDL-C), low-density lipoprotein cholesterol (LDL-C) and triglycerides will be measured using a colorimetric method using the Cobas Mira Plus analyzer (Horiba, ABX, France).

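### The p<0.10 entry rule does not exempt the plaque-burden exposure, so the main hypothesis can be left without an adjusted estimate

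*SAP*

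**What the plan says.** All statistical text is in the single unnumbered section of the SAP.

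- **Outcome.** "The primary outcome of the study will be the presence of white matter hyperintensities (WMH) progression", meaning one or more new lesions at 18 months.
- **Hypothesis and contrast.** "Our main hypothesis is that subjects with a high plaque burden will experience the highest progression of WMH", with the coding fixed as follows: "We will analyze the highest tertile of carotid plaques burden in terms of plaque volume versus others".
- **Sample size.** "We calculated the sample size for multivariate logistic regression analysis with a power of 0.8 and an alpha of 0.05". The inputs are 33% high burden, 50% versus 15% progression, and 58 patients.
- **Adjusted model.** "A multivariate regression analysis was then performed to identify factors that independently influence the burden of WMH in terms of number and volume".
- **Entry rule.** "All variables associating to WMH burden with a $p<0.10$ will be included in the multivariable model". It follows a list of two-group, rank-correlation and contingency-table tests, so the screen is in effect unadjusted, although the SAP does not use that word.

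Neither document names a variable that is always included. Treatment is available as a covariate: the Protocol, under Clinical evaluation and biochemical measurements, states that "The history will be focused on the identification of cardiovascular risk factors (CVRFs) and of current treatment".

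**The concern.** The study is sized for a multivariable test of one pre-specified exposure, yet the only stated way into a multivariable model depends on that exposure's own unadjusted p-value. Where plaque burden misses 0.10, the plan as written produces no adjusted estimate and no confidence interval. A report that plaque burden was not an independent predictor could then mean that it was never entered.

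An unadjusted screen is weakest when two effects oppose each other. If patients with more plaque were more often treated, and treatment went with less WMH, the crude plaque association would shrink and could be screened out although the adjusted one is clear.

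**Working it through.** **Inputs from the SAP.** Two-thirds/one-third split (33% high burden, so 19 versus 39 of 58), progression 50% versus 15%, alpha 0.05, power 0.80, screen at 0.10. Sidedness is not stated; two-sided reproduces the plan's figure.

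**1. The plan's own number.** Hsieh's formula for logistic regression on one binary covariate, with B = 0.33:

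- Overall rate P = 0.67×0.15 + 0.33×0.50 = 0.2655
- First term: 1.960×√(0.2655×0.7345/0.33) = 1.507
- Second term: 0.842×√(0.15×0.85 + 0.50×0.50×0.67/0.33) = 0.671
- N = (1.507 + 0.671)² / (0.35²×0.67) = 4.741/0.0821 = 57.8, rounded up to 58

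The stated 58 is reproduced, with no inflation for correlation between plaque and other covariates. Expected progressors: 19×0.50 + 39×0.15 = 15.35, about 15.

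**2. Chance that plaque fails the screen on the plan's own assumptions.**

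- Pooled rate 15.35/58 = 0.265
- Null SE = √(0.265×0.735×(1/19 + 1/39)) = 0.123
- Alternative SE = √(0.25/19 + 0.1275/39) = 0.128
- Pass probability = Φ((0.35 − 1.645×0.1234)/0.1282) = Φ(1.147) = 0.874, so 12.6% fail

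Summing the binomial probabilities of every possible 2×2 table with p≥0.10 gives 11.5% failing by Pearson chi-squared and 14.5% by Fisher's exact test. Hence about 11–15%. This depends only on the crude rates, so it holds with or without masking as long as 50% versus 15% is right.

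**3. How many failures cost a significant adjusted result.** Simulation of 4,000 studies per row: N = 58, 19 versus 39, screen at 0.10, then a logistic likelihood-ratio test of plaque adjusted for one treatment variable. The conditional plaque odds ratio is (0.50/0.50)/(0.15/0.85) = 5.67, and the crude low-burden rate is held at 15%. Treatment prevalences and odds ratios are assumptions; the documents give none. *Lost* means p<0.05 when plaque is forced in, but screened out. Paired entries are Pearson/Fisher.

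| Treatment OR | Treated, high vs other burden | Fails screen (%) | Power if forced in (%) | Lost (%) |
|---|---|---|---|---|
| 1.0 | 50 vs 50 | 11/14 | 81 | 0.1/0.2 |
| 0.50 | 70 vs 40 | 22/26 | 74 | 2.4/4.1 |
| 0.50 | 80 vs 30 | 28/34 | 65 | 4.5/7.0 |
| 0.50 | 90 vs 30 | 35/41 | 56 | 6.3/8.8 |
| 0.33 | 70 vs 40 | 30/36 | 71 | 6.0/9.3 |
| 0.33 | 80 vs 30 | 45/49 | 61 | 12.2/15.0 |
| 0.33 | 90 vs 30 | 52/57 | 52 | 12.6/15.6 |
| 0.20 | 70 vs 40 | 48/52 | 64 | 12.9/16.3 |
| 0.20 | 80 vs 30 | 65/70 | 54 | 21.5/25.1 |
| 0.20 | 90 vs 30 | 74/78 | 45 | 22.4/24.9 |

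In the masked rows the crude high-burden rate falls from 50% to between 44% and 25%. They therefore describe a study whose crude difference is smaller than planned.

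**4. Burden model, to which the rule's wording refers.** Mann-Whitney screen, then a linear model on log lesion volume. Assumed, and in neither document: residual SD 1.25, high-burden ratio 2.65, treatment in 70–80% versus 40% lowering volume 1.5- to 2-fold. Power with plaque and treatment forced in, versus screened, was 73 vs 65, 71 vs 62, 75 vs 57 and 70 vs 48%. Plaque was dropped in 25–43% of studies, but only 5–16% of studies were both dropped and significant when forced in. With treatment unrelated to plaque the power loss was 1–3 points.

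**5. Direction reversed.** If treated patients have more WMH (70 vs 40%, 1.5-fold; 80 vs 40%, 2-fold), power was 74 and 70% forced versus 77 and 71% screened, and plaque was dropped in 9 and 5% of studies. The loss disappears.

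**The case against.** **The rule may not be exclusive.** The SAP says that variables below 0.10 go in; it does not say that others stay out. It also commits to the tertile contrast, next to the logistic sample size. A reader could fairly take the tertile as always tested. This stands in part: exclusivity is an inference. But fixing the contrast does not say that it bypasses the screen, and no other route into the model is given.

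**The rule and the hypothesis concern different outcomes.** The screen is worded for burden; the hypothesis and sample size are for binary progression. This is correct. Applying the rule to progression is an extension, made because no progression rule exists.

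**The masking story needs one direction.** Under Clinical evaluation, the Protocol counts current blood-pressure medication as diagnostic of hypertension and lipid-lowering therapy towards hypercholesterolemia. Treatment therefore also marks the risk factor, and treated patients may have more WMH. This stands; masking is a possibility, not a finding.

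**Stronger readings that a reader might infer.**

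- *That the whole gap between forced and screened power comes from excluding plaque.* It does not. Most dropped studies would not have been significant anyway, and much of the gap comes from omitting treatment. In the logistic case with odds ratio 0.5 and 70 versus 40% treated, power falls from 75 to 67%, but only about 3 points are studies in which plaque was dropped.
- *That the screen materially exaggerates the reported plaque effect.* In the masked burden scenarios the mean reported ratio was 2.66–2.79 against a true 2.65. It reached about 2.9 only where treatment was unrelated to plaque, and there the power loss is small.
- *That the screen inflates false positives.* For a positive confounder such as age, the rate under the null was 3.5–5%.

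**Conclusion.** The point holds in a limited form. The SAP's only entry rule does not protect the exposure on which its hypothesis and sample size rest. Read as the sole route and carried to progression, it leaves that exposure without an adjusted estimate in about 11–15% of studies under the plan's own rates. This figure needs no masking assumption.

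The cost in significant adjusted results is negligible without masking, roughly 2–16 percentage points of studies under mild to moderate masking, and up to about 25 in the most extreme case tried. Those figures rest on assumed prevalences and effects, and they vanish if treatment goes with more WMH. The documents do not support a claim that masking by treatment is present, or that plaque will be wrongly excluded. The case for the change rests on the pre-specified hypothesis always receiving its adjusted estimate.

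**What to change.** Add to the SAP: *Top-tertile plaque volume versus the other two tertiles is kept in the multivariable logistic model for WMH progression, and in the models for WMH number and volume, whatever its univariable p-value. Its adjusted estimate and confidence interval are always reported. The p<0.10 screen applies only to the other candidate variables.*

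The outcome must be named, because a sentence about the multivariable model alone would leave the progression test unspecified. Any further forced covariates, for example age or one merged treatment indicator, should number at most one or two and be chosen in advance on subject-matter grounds, since only about 15 progressors are expected. Whether to force any is a judgement; keeping the exposure in does not depend on it.

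Cost: one or two added sentences, and one degree of freedom in studies where plaque would otherwise have been screened out. The stated N of 58 does not change. Correlation between plaque and an added covariate would lower adjusted power below the nominal 80%, as the masked rows of the table show.
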